9.1. Study Design

VIR-Life is a prospective non-interventional multicenter cohort post-authorization safety study of an individual case series. The study will follow patients who have been prospectively observed through three years in the GEMINIS NIS for additional three years. The study is designed as a multicenter, non-interventional observational study, in accordance with the German Drug Act (§4 Abs 23 Satz 3 AMG, and §4 Abs 34 AMG, §63f AMG).

9.1.1. Rationale for the study design

Tenofovir disoproxil 245 mg (as Fumarate; TDF; Viread[®]), is licensed in the EU for the treatment of chronic Hepatitis B since 2008. The efficacy and safety of TDF have been reported in hepatitis B virus mono-infection in HBeAg-negative patients and HBeAg-positive patients [24,26]. In two phase III studies evaluating the efficacy and safety of TDF vs. Adefovir dipivoxil, control of viral load was significantly higher in the TDF arm compared to the Adefovir arm. At 48 weeks, the proportions of patients with a viral load < 400 copies/mL were 93% vs. 63% for study GS-US-174-0102 (HBeAg-negative) and 76% vs. 13% for study GS-US-174-0103 (HBeAg-positive), respectively (p< 0.001 for the 2 studies; ITT analysis). Furthermore, in study GS-US-174-0103, the rate of negativation of HBsAg was significantly higher in the TDF arm (3.2% vs 0%; p = 0.018)[24]. No HBV resistance mutation has been reported in patients treated with TDF and the safety profile of TDF is satisfactory [24–26,29].

However, patients included in phase III clinical trials are selected according to strict, inclusion and exclusion criteria. These RCTs are designed to investigate the efficacy and safety of a drug in predefined populations, therefore providing high internal validity. The characteristics of patients treated in routine clinical practice after marketing of the product can therefore differ considerably from those on which the product was evaluated. Special subpopulations excluded from therapeutic trials may be treated: elderly, comorbidities, patients previously treated for hepatitis B, etc.

Data generated in real-life settings allows for investigating the external validity of the effects observed in RCTs. The treatment outcomes in real-life of the drug can be investigated in observational studies such as a non-interventional cohort study.

VIR-Life is designed to evaluate the treatment outcomes and the patterns of use of Viread[®] in routine clinical practice in patients infected by the hepatitis B virus in Germany. VIR-Life is a 3-year roll-over non-interventional cohort study from GEMINIS, the first non-interventional cohort study on the use of Viread[®] in Germany. VIR-Life will complete these data, concerning safety, clinical, virological, biochemical, serological outcomes and patterns of use of Viread[®] in patients with chronic HBV infection in clinical practice for a total of 6 years.

9.2. Setting / Study Population

VIR-Life is a roll-over study in adult, HBV-mono-infected CHB patients who started CHB treatment with Viread[®] in GEMINIS. Patients in GEMINIS, and therefore now in VIR-Life, are collected nationwide in a real-life setting at approximately 25 of the initial 35 GEMINIS sites. The study sites are either office based physicians with hepatological focus or hospitals with dedicated hepatological outpatient care units.

If the physician decided to treat and document a patient monoinfected with HBV with Viread[®] in GEMINIS and later in VIR-Life, he/she can document the course of the therapy (at months 48, 60 and 72) within the scope of a non-interventional study (NIS).

Eligibility criteria:

Patients completing 3 years in GEMINIS and still receiving a Viread[®]-containing regimen may roll over into this study

9.2.1. Rationale for the selection of the study sites

In Germany approx. 80% of the CHB patients under treatment are followed up by specialized centers. To obtain a representative view on the medical practice of CHB patients in Germany, out of the 35 specialized hepatology sites from GEMINIS approximately 25 centers which enrolled at least 5 patients into GEMINIS will be invited to participate in VIR-Life. These sites are primarily gastroenterological offices with designated focus on hepatology, as well as some of the largest hospital liver outpatient care units. Disproportionate distribution of sites across the federal states of Germany can be explained by unequal prevalence of chronic hepatitis B (e.g. East/West, or rural/-urban disproportion of CHB).

9.2.2. Rationale for the patient number

The target number of 250 patients, followed up at approximately 25 well distributed study sites, supports representativeness of the drawn sample to the overall CHB-population currently treated with Viread[®] in Germany. It is expected that the patient number of 250 supports conclusions on the treatment results in major subpopulations (e.g., elderly patients). The 6 year long term follow up data from 250 patients is expected to contribute to the safety profile of Viread in CHB patients in a real life setting.

9.2.3. Prevention of bias

- In GEMINIS all centers with large (>100) CHB patient volume were invited to participate in the study, however, disproportionate distributions across the federal states of Germany were expected due to the unequal distribution of prevalence of chronic hepatitis B.
- GEMINIS was open for all patients chronically (mono-) infected with Hepatitis B Virus, potentially eligible for treatment under current guidelines as stated earlier in the introduction section. Enrollment was allowed for to up to 400 patients treated with Viread[®].
- To combat selection bias the participating sites in GEMINIS were asked to enroll every single new patient qualifying for inclusion until the NIS is fully recruited.
- For VIR-Life, all eligible GEMINIS patients remaining in the 25 participating sites are asked to be rolled over into the VIR-Life study
- For all eligible patients not enrolling into VIR-Life the sites have to document respective reasons (lost to follow-up, no signed ICF, death).

9.3. Variables

In this non-interventional post-authorization safety study the time the subject has taken Viread[®] is the exposure of interest. Outcome variables are the collected clinical and laboratory parameters, i.e.:

Primary outcome variable:

- Virology
 - Serum HBV-DNA

Secondary outcome parameters are:

- Serology
 - HBeAg/anti-HBe (qualitative)
 - HBsAg/anti-HBs (qualitative)
- Biochemistry parameter
 - o ALT
- Renal function parameters

- Serum creatinine
- Creatinine Clearance (estimated via Cockcroft-Gault, MDRD or CKD Epi formula)
- Serum phosphorus
- Liver synthesis parameters
 - o Albumin
 - o Bilirubin
 - Thrombocytes
 - Prothrombin time [i.e. Quick-Value]
- Safety parameters
 - Adverse events
 - Special Situations; pregnancies, medication error, abuse, misuse, overdose, lack of effect, adverse events in infants following exposure from breastfeeding and adverse events associated with product complaints
- Incident cases of co-infections
 - o HIV
 - o HCV
 - o HDV
- Co-morbidities (incident and prevalent cases)
 - o Ascites
 - o Jaundice
 - Diabetes mellitus
 - Lipometabolic disorders
 - o Coronary heart disease
 - Hypertension

- Alcohol consumption per week
- Liver histology and HCC
 - Liver biopsy results
 - o Fibroscan
 - o HCC
- Dosing and dose alterations
- Combination therapy
- Treatment discontinuations
 - Patients discontinuing Viread should not be discontinued from study follow up. All study variables in these patients shall be documented in VIR-life until month 72

9.4. Data Sources

The conduct of a non-interventional study (NIS) requires, according to definition of a "non-interventional study" in terms of Guideline on good pharmacovigilance practices (GVP) – Module VIII (Rev 1), that the protocol does not stipulate or dictate on the diagnosis, therapeutic decisions and follow-up of the individual patient. The study only observes and collects the use of a drug and the corresponding clinical outcome by the treating physician in the specific indication.

Clinical data is collected from the physician's documentation of the patient's visit in patient medical records that is closest to the documentation time point (month 48, 60 and 72), each +/- 3 months. Primary data sources are electronic medical records, where available or paper records at the participating sites. This data will then be manually transcribed by the investigator into electronic case record form (eCRF).

In this non-interventional follow up study, the following findings are of special interest and information will be collected accordingly:

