4. PROTOCOL SYNOPSIS/ABSTRACT

Gilead Sciences GmbH [name] Germany

Study Title:	VIR-Life : Prospective assessment of the real-life treatment outcomes of six years of Viread [®] in CHB following-up on the German Multicenter Non-Interventional Study GEMINIS		
Rationale and Background:	The efficacy and safety of TDF is well established by data from randomized controlled trials (RCTs) in various patient populations, such as the Gilead sponsored studies GS-US-174-102 and GS-US-174-103 in treatment naïve patients, or GS-US-174-106, GS-US-174-115 and GS-US-174-121 in patients previously treated with oral antivirals.		
	Clinical studies, such as RCT's investigate the efficacy and safety of a drug in predefined populations, therefore providing high internal validity. Data generated in real-life settings allows for investigating the external validity of the effects seen in RCTs. Thus the real-life treatment outcomes of the drug can be investigated in observational studies such as non-interventional studies (NIS).		
	The real-life treatment outcomes of Viread [®] have been investigated in GEMINIS for a period of 3 years. VIR-Life is the roll-over non- interventional study from GEMINIS to allow the prospective evaluation of the real-life treatment outcomes for additional 3 years.		
Research Question and	The primary objective of this study is as follows:		
Objectives:	• Prospectively describe the virological response, defined as HBV- DNA concentration, during 6 years Viread [®] treatment for CHB in a real life setting.		
	The secondary objectives of this study are to evaluate the:		
	• Safety and tolerability of 6 years of Viread [®] in CHB in a real life setting		
	 Adverse drug reactions (AR) (unrelated Adverse Events (AEs) will also be listed in the report) 		
	• Renal safety		
	Estimated creatinine clearance (eCrCl)		
	Serum creatinine level		

Serum phosphorus level			
	• Histological improvement of the liver		
Study Design:	Prospective non-interventional multicenter cohort post-authorization safety study (single treatment case series)		
Population / Setting:	Roll-over study in adult, HBV-mono-infected CHB patients who started CHB treatment with Viread [®] in GEMINIS		
Duration of Study:	3 years after rolling over from GEMINIS		
Variables: Documentation of routine visits at month 48, 60 and 72, covering following parameters (if available):			

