ALT < ULN* HBeAg-loss	71%	77 %		
HBeAg-seroconversion HBsAg-loss**(HBeAg+ at baseline)	19 % 5.1 %			
HBsAg-loss (HBeAg- at baseline) $2/226$ with documented HBsAg*ULN: Male ≤ 43 IU/L, female ≤ 34 IU/L; ** Kaplan Meier Estimate (Cumulative probability in patients with documented HBsAg)				

Table 2: 2 years virological, serological and biochemical results[28]

Tuble of of cume clearance aaring fonon ap	Table 3:	Creatine-clearance	during	follow-up
--	----------	---------------------------	--------	-----------

Estimated CrCl (Cockcroft-Gault)	Baseline (n = 361)	Month 6 (n = 299)	Month 12 (n = 289)	Month 24 (n = 255)
Mean [ml/min] (SD)	106.9 (31.6)	105.9 (33.8)	104.7 (31.7)	102.2 (31.3)
Mean change [ml/min] (SD)		-1.4 (16.1)	-3.2 (16.2)	-3.4 (15.4)

8. **RESEARCH QUESTION AND OBJECTIVES**

Clinical studies, such as RCT's investigate the efficacy and safety of a drug in predefined populations, therefore providing high internal validity. Data generated in real-life settings allows for investigating the external validity of the effects seen in RCTs. Thus the real-life treatment outcomes of the drug can be investigated in observational studies such as non-interventional studies (NIS).

The real-life treatment outcomes of Viread[®] have been investigated in GEMINIS for a period of 3 years. VIR-Life is the roll-over non-interventional study from GEMINIS to allow for the continued prospective evaluation of the real-life treatment outcomes for additional 3 years.

The primary objective of this study is as follows:

• Prospectively describe the virological response, defined as HBV-DNA concentration, during 6 years Viread[®] treatment for CHB in a real life setting.

The secondary objectives of this study are to evaluate the:

- To describe the safety and tolerability of 6 years of Viread[®] in CHB in a real life setting, and report the following:
 - Adverse drug reactions (ADR) (unrelated Adverse Events (AEs) will also be listed in the report)
 - Renal safety
 - Estimated creatinine clearance (eCrCl)
 - Serum creatinine level
 - Serum phosphorus level
- Histological improvement of the liver

9. **RESEARCH METHODS**

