9.9. Limitations of the research methods

In a non-interventional study all decisions on the management of the patient are made solely by the treating physician. This also includes the frequency of the evaluation of lab values and other collected variables. Documentation of study variables must not be made obligatory. Missing data of unpredictable extent can occur.

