11.2.1. Assessment of Causality for Study Drugs and Procedures

The investigator or qualified subinvestigator is responsible for assessing the relationship to drug therapy using clinical judgment and the following considerations:

- No: Evidence exists that the AE has an etiology other than the drug. For SAEs, an alternative causality must be provided (eg, preexisting condition, underlying disease, intercurrent illness, concomitant medication).
- Yes: A temporal relationship exists between the AE onset and administration of the drug that cannot be readily explained by the subject's clinical state or concomitant therapies. Or, the AE appears with some degree of certainty to be related, based on the known therapeutic and pharmacologic actions or AE profile of the drug. In case of cessation or reduction of the dose, the AE may abate or resolve and it may reappear upon rechallenge.

It should be emphasized that ineffective treatment should not be considered as causally related in the context of AE reporting.

11.3. Investigator Requirements and Instructions for Reporting Adverse Events and Serious Adverse Events to the CRO

During the defined study period (month 36 to months 72), each investigator has to document all Adverse Events he becomes aware of including seriousness and causality in the eCRF system within 24 hours. These are automatically forwarded via the eCRF system to the CRO safety department.

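### Section 9.4 ties laboratory data to the single visit nearest months 48, 60 and 72, so HBV-DNA and renal results from other visits in the same window are lost

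*Protocol*

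**What the plan says.** Section 9.4 (Data Sources) defines the unit of collection: "Clinical data is collected from the physician's documentation of the patient's visit in patient medical records", and the visit meant is the one "closest to the documentation time point (month 48, 60 and 72), each +/- 3 months". The synopsis describes the same scheme as "Documentation of routine visits at month 48, 60 and 72", with parameters recorded if available. Section 9.4.2 lists the parameters for those three time points. No section says what to do when the nearest visit lacks a test that another visit in the window contains.

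The primary objective (synopsis and Section 8) is to "Prospectively describe the virological response, defined as HBV- DNA concentration, during 6 years Viread". Creatinine, estimated creatinine clearance and phosphorus are the named renal safety measures.

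Section 9.9 leaves testing to the treating physician ("This also includes the frequency of the evaluation of lab values and other collected variables") and accepts the consequence: "Missing data of unpredictable extent can occur". Sections 9.5 and 9.10 fix the sample size by the number of patients available to roll over, planned at 250.

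**The concern.** The rule selects a visit first and then takes whatever that visit contains. Physicians decide which tests to order and when, so the visit nearest month 48 may hold a clinical review without HBV-DNA while a visit some weeks away, still inside the window, holds the result. Followed as written, the site leaves the HBV-DNA field empty although the value is in the chart.

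Section 9.9 explains missing values by tests that were never ordered. It does not account for tests that were done and then passed over by the collection rule. That second kind of loss is avoidable, and it falls on the primary outcome and the renal parameters. Because patients cannot be added beyond the roll-over pool, completeness within each patient is the main remaining way to keep precision. Sites that read the sentence differently would also collect differently.

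**Working it through.** The Protocol gives no figure for this loss, and 250 is not derived from a formula, so there is nothing to reproduce. The check has two parts.

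**1. Reading the rule**

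- Section 9.4 refers to one visit per time point, with windows 45–51, 57–63 and 69–75 months.
- The synopsis and Section 9.4.2 use the same time points and add no fallback.
- The non-interventional principle in Section 9.4 bars the protocol from dictating diagnosis, therapy or follow-up. It does not bar copying a result that is already in the record, and the investigator already transcribes from that record.

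The loss therefore follows from the wording, and non-interventional status does not require it.

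**2. Illustrating the size**

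Let *q* be the probability that a given visit carries the test, and *k* the number of visits in the window.

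- Nearest visit only: missing share = 1 − *q*.
- Nearest value per parameter, visits independent: missing share = (1 − *q*)^*k*.

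The only availability figures in the Protocol are the creatinine clearance counts in Table 3 (Section 7.3), set against 400 enrolled:

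- Baseline: 361/400 = 0.9025, before any drop-out.
- Month 24: 255/400 = 0.6375. This mixes drop-out with tests not done. VIR-Life admits only patients who completed three years and are still on treatment (Section 9.2), so it overstates the loss from untested visits.

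The value *k* = 2 is an assumption; the Protocol does not state visit frequency.

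| *q* | Nearest visit only | Nearest value, *k* = 2 | Values recovered per time point, of 250 |
|---|---|---|---|
| 0.9025 | 0.0975 (about 10%) | 0.0975² = 0.0095 (about 1%) | 250 × 0.0880 = 22 |
| 0.6375 | 0.3625 (about 36%) | 0.3625² = 0.1314 (about 13%) | 250 × 0.2311 = 58 |

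With *k* = 1 the two rules coincide and the gain is zero.

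Independence also matters. If some physicians rarely order the test, so that the second visit lacks it whenever the first does, the gain again falls to zero. If testing alternates between visits, the chance that both lack it is max(0, 1 − 2*q*) = 0 for either *q*, and the gain is larger than shown. The 250 is the planned size and takes no account of attrition after roll-over.

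**The case against.** The strongest case on the other side is that this is at most a clarification. The Protocol does not say how often patients are seen, so the gain may be nil. The eCRF instructions are not shown and may already tell sites to use another visit in the window. Taking parameters from different visits can also separate values that belong together, notably weight and creatinine for the Cockcroft-Gault estimate. All of this stands as a limit on the size of the point and on how the fix is worded. It does not remove the point: the rule as written in the Protocol has no fallback.

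A reader might infer three stronger things that the document does not support.

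- **That more than half of follow-up is discarded.** The intervals outside the windows are 9 + 6 + 6 = 21 months. That is 58% of the 36 months in the study period of Section 11.3 ("During the defined study period (month 36 to months 72") and 54% of the 39 months to month 75. This is calendar time, not lost data, and any study with annual windows has such gaps. Adverse events are recorded throughout the study period (Section 11.3). They include laboratory abnormalities that need intervention or lead to a treatment change (Section 11.1.3). Lack of effect is reported as a special situation (Section 11.4), and dose changes and discontinuations are collected (Section 9.3). Resolved abnormalities that met none of these criteria can still go unseen.
- **That the rule biases results towards stable suppression and stable renal function.** Choosing a visit by date does not depend on the laboratory value. The objective describes HBV-DNA concentration over time and names no endpoint of ever having rebounded. Annual sampling has lower resolution, which is not in itself bias.
- **That yearly highest and lowest values should be added.** Extremes depend on how often a patient is tested, which the physician decides (Section 9.9). Frequently tested patients would tend to look worse. The GEMINIS results shown in Section 7.3 contain no counterpart.

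**Conclusion.** The concern holds in a limited form. The wording of Section 9.4 can lose HBV-DNA, creatinine and phosphorus results that exist inside the window, and nothing in the Protocol prevents this. The mechanism is certain on a literal reading, but its size is not known. Under two independent visits per window the illustration runs from 10% down to 1% missing (*q* about 0.90) to 36% down to 13% (*q* about 0.64). The first case is the better guide because it contains no drop-out. The gain is zero if only one visit falls in the window. This is a cheap improvement to data completeness. It does not show that the planned results would be biased or that the objective cannot be met.

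**What to change.** Reword the collection rule in Section 9.4 along these lines: *For each parameter, the value closest to month 48, 60 or 72 within +/- 3 months is documented with its date, even if from a different visit.* Add that the weight used for the Cockcroft-Gault estimate is the one recorded as close as possible to the creatinine date. Align the synopsis wording with this.

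The cost is a date for each laboratory value in the eCRF, slightly more transcription, and values within one time point that may come from different days. No additional test or visit is requested, so the study stays non-interventional. If the eCRF instructions already work this way, the change only brings the Protocol text into line with them.

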9.4.1. Baseline

VIR-life is the extended follow up of GEMINIS. Therefore, VIR-life baseline data is the data that was collected at GEMINS baseline.

9.4.2. During VIR-Life follow up and at end of follow up (month 48, 60 and 72):

- HBV- virology and serology parameters
- Biochemical serum-parameters
 - ALT
- Renal safety parameters
 - Serum creatinine, eCrCl, serum phosphorus
- Liver synthesis parameters
 - Albumin, bilirubin, thrombocytes, prothrombin time (Quick-Value)
- Liver histology, elastography, incident HCC
- Co-morbidities, Co-infections, alcohol consumption
- Adverse events
- Special Situations; pregnancies, medication error, abuse, misuse, overdose, lack of effect, adverse events in infants following breastfeeding, and adverse events associated with product complaints
- Dosing of Viread[®]
- Combination therapy
- Reason for discontinuation of Viread[®], if applicable

9.5. Study Size

The planned study size is 250 patients. This number is pre-specified by the number of eligible patients to be rolled over from GEMINIS in the participating 25 study sites.

To maximize the possible sample size, all eligible patients in the participating sites shall be rolled over into the study.

